6.4.9. Changes in mean daily steroid dose (Observed) (Table 3.12x)

Analyzed: Efficacy analysis population

Analysis details: For average daily steroid dose, summary statistics will be calculated over time.

Calculation items: Mean daily steroid dose, change, and percent change

Chronological order: Weeks 4, 8, 12, 16, 20, 24, 28, 32, 36, 40, 44, 48, and 52

6.4.10. Change from baseline in average daily steroid dose (Table 3.13)

Analyzed: Efficacy analysis population

Analysis details: The proportion of patients leading to the following calculation items will be calculated in chronological order.

Calculation items: 1. Mean daily steroid dose decreased

2. Mean daily steroid dose increased

3. Decrease from baseline average daily steroid dose >7.5 mg/day to ≤ 7.5 mg/day

4. Increase from baseline average daily steroid dose ≤ 7.5 mg/day to >7.5 mg/day

Chronological order: Weeks 4, 8, 12, 16, 20, 24, 28, 32, 36, 40, 44, 48, and 52

6.4.11. Cumulative steroid dose (Table 3.14)

Analyzed: Efficacy analysis population

Analysis details: For cumulative steroid dose, summary statistics will be calculated.

6.4.12. Time-course plots for the proportion of responders in SELENA SLEDAI score, PGA score, and LLDAS (Figure 3.0x)

Analyzed:	Efficacy analysis population
Analysis details:	For each efficacy endpoint (SELENA SLEDAI score, PGA score, LLDAS), responder rates will be calculated over time and bar charts will be prepared. The denominator for the responder rate is the number of patients. Additionally, for the Lupus Impact Tracker, a bar chart of mean + standard deviation will be produced over time.
Chronological order:	Week 24, Week 52, and at discontinuation/completion (LOCF) (SELENA SLEDAI score, PGA score, LLDAS)

6.4.13. Time Course Plot of Lupus Impact Tracker Score (Figure 3.04)

Analyzed:	Efficacy analysis population
Analysis details:	For the Lupus Impact Tracker scores, bar charts of mean + standard deviation will be prepared over time for each item.
Chronological order:	Baseline, Week 24, and Week 52, and at discontinuation/completion (LOCF)

6.4.14. Time course of percent improvement in steroid group (Figure 3.05)

Analyzed:	Efficacy analysis population
Analysis details:	For the improvement rate of steroid treatment, Kaplan-Meier plots will be calculated with the time point when the dose of steroid becomes 7.5 mg/day or less or the dose of steroid from baseline becomes 50% or less as an event.
CONDITION:	Patients with baseline average daily steroid dose >7.5 mg/day will be included.

6.4.15. Changes in laboratory values (Anti-dsDNA, C3, C4, CH50, protein/creatinine ratio) (mean + SD) (Figure 3.06x)

Analyzed:	Efficacy analysis population
Analysis details:	For anti-dsDNA antibody, C3, C4, CH50, and protein/creatinine ratio, time-course plots of mean + standard deviation will be prepared for each item.
Chronological order:	Baseline, Week 24, and Week 52, and at discontinuation/completion (LOCF)

6.4.16. Changes in the proportion of patients receiving immunosuppressants (Table 3.15)

Analyzed:	Efficacy analysis population
Analysis details:	The number of target patients (number of patients using the drug) and the usage rate will be calculated by immunosuppressant and immunosuppressant (biologic drug) for each drug code (GSKdrug) and generic name. The denominator of the usage rate is the number of patients in each analysis set.
Chronological order:	Prior treatment, Separate volume 1, Separate volume 2

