Under the assumption that the incidence rate of the serious infections is 5.3% as a threshold on the basis of the results of the phase III international joint studies, 553 patients are required to monitor the incidence rate in the post-marketing surveillance with estimation accuracy that enables a power for the 5.3% threshold to be $\geq 80\%$ in case where the real risk exists 1.5 times or more of the threshold. It is considered possible to evaluate occurrence of the serious infections in the special DUI (SDUI) having 600 patients as a target sample size.

The incidence rate of ADRs occurring in one patient was 0.2% in the phase III international joint studies. The power to detect an ADR whose incidence rate of 0.2% is 69.9% in at least one patient out of 600 patients.

5. Planned Number of Medical Institutions by Department

All medical institutions where Benlysta is prescribed (except medical institutions that prescribe Benlysta only for patients aged <15 years since approval for paediatric dosage)

6. Study Period

1. Study conduct

Study period : launch date of Benlysta to three months after termination of the observation period in patients eligible for case report form (CRF) collection (period of the follow-up investigation, if conducted) or lifting date of approval conditions, whichever comes later

Observation period :

The observation period per patient will be 52 weeks from the start of Benlysta administration.

For patients who continue administration at the end of the observation period, conduct the two-year follow-up investigation as much as possible, and monitor occurrence of AEs leading to death, serious infections, PML, and MT.

If a patient has withdrawn from /terminated administration of Benlysta, it will be until the withdrawal/termination.

Scheduled enrolment period : launch date of Benlysta to six months after lifting of approval conditions

Patients are eligible for CRF collection when starting Benlysta administration by 31 October, 2018, and CRFs will be collected as required when patients start the administration since 1 November, 2018. Additionally, patients are eligible for enrolment when starting the administration by the acknowledgment of the report at a committee meeting, where the all-case investigation-related conditions for approval are lifted (except patients aged <15 years who start Benlysta administration since approval for paediatric dosage), and enrolment will continue.

2. Study end

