*: Described in “2. IMPORTANT PRECAUTIONS (7)” in the Package Insert for subcutaneous use.

5. Pre-treatment drugs intended for SLE
Presence or absence of drugs intended for SLE and name of drugs, from 4 weeks before the start of administration to the day before the start
Biological preparations and cyclophosphamide (intravenous injection) except Benlysta will be monitored from 24 weeks before the start of administration to the day before the start.
6. Administration status of Benlysta
Administration route of Benlysta during the observation period (Regarding subcutaneous injection, record any of the autoinjector or syringe.), single dose, duration of administration, administration interval during each period, dosing frequency during each period, reason for revision of the Dosage and Administration and drug withdrawal
7. Concomitant drugs (SLE drugs)
Presence or absence of concomitant drugs (SLE drugs), name of drugs, during the observation period
For systemic steroids, the information about the presence or absence of concomitant use, name of drugs, administration route, daily dose (dose, unit), duration of administration, reason for revision of the Dosage and Administration will be collected. For cyclophosphamide, the information about the presence or absence of concomitant use and administration route will be collected.
8. Concomitant drugs (except SLE drugs)
Presence or absence of concomitant drugs intended for SLE (except SLE drugs), name of drugs, reason for administration, during the observation period
9. Concomitant therapies intended for SLE (except drugs)
Presence or absence of concomitant therapies intended for SLE (except drugs), name of therapies, during the observation period
10. Vaccination
Presence or absence of vaccination, type of vaccine, date of vaccination, during the observation period
11. Course of clinical symptoms
The information about the following items will be collected.

1) Safety of Estrogens in Lupus Erythematosus National Assessment SLE Disease Activity Index (SELENA SLEDAI)

Record the presence or absence of assessment, assessment date, results of assessment at the start date of administration*, Week 24 and 52 after the start of administration, or withdrawal/termination (See Appendix 1).

* : If no information is available about the results of assessment at the start date of administration, record the information closest to the start date in the results of SLE diagnosis to the start date.

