4.2. Analysis sets/sites

Item	Definition
Registered sites	Sites for all registered patients (patients eligible for registration). Sites with patients registered before the data lock date (excluding duplicate site codes).
Enrolled patients	Patients enrolled within the enrollment period specified in the protocol (from December 13, 2017 to the date of lifting of approval conditions) (registration-eligible patients). Subjects with an enrollment date before the data lock date.
Patients with locked CRF	All registered patients whose CRFs were collected and locked. Cases that have a recall date and a processing completion date and the processing completion date is before the data lock date.
Safety analysis population	Patients with locked CRFs who do not correspond to patients excluded from the safety analysis set (see 4.3.1)
Efficacy analysis population	Patients in the safety analysis set who are not excluded from the efficacy analysis set (see 4.3.2)
CRF collection target patients (Approval condition lifting)	Reports on registered patients whose CRFs were collected and patients eligible for CRF collection were identified (administration of this drug was started by October 31, 2018). The start date of administration of this drug (registration form) shall be the date of registration form.
Sites that can publish	PMW sites that are “11 _ Publication allowed (already concluded) ” or “ 13_ Publication allowed (no change required) ” and sites that are confirmed as “21 _ Being confirmed ” to be “ Publication allowed ”

Item	Definition
Subjects who completed the observation period (Interim analysis)	
< Subjects falling under Population A >
 
Disclosure-ready patients meeting any of the following conditions among patients treated with this drug before October 31, 2018 at study sites
 
 • Completed up to Week 52: Separate Volume 1 (official approval) and Separate Volume 2 (official approval) • Completed as discontinued: Volume 1 (official approval) in which the reason for discontinuation is described is official approval (excluding official approval of Volume 2 only) • Completed as discontinued (logic assessment): Separate volume 1 (official approval) and Separate volume 2 is “Unnecessary ” or“ Unable to collect ” 
< Subjects falling under Population B >
 
This falls under “patients with depression-related events ” among patients whose CRFs were additionally collected and are specified in a separate document.

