4.17. Handling of fixed cases by volume

Data of fixed cases and each volume will be used as CRF data. (If Volume 1 is locked, the patient will be classified as a "locked patient," but data from CRFs from which subsequent volumes are not locked will not be used in analyses.)

For tabulation of "subjects who completed the observation period," refer to the definition of "subjects who completed the observation period (interim analysis)" in analysis sets/sites in 4.2.

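### Table 3.15 (SAP 6.4.16) divides Volume 2 immunosuppressant use by the whole efficacy set, so patients with no locked Volume 2 dilute the rate and produce a false fall

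*SAP*

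**What the plan says.** SAP 6.4.16 names one population, "Efficacy analysis population", and one denominator: "The denominator of the usage rate is the number of patients in each analysis set". It lists three periods: "Prior treatment, Separate volume 1, Separate volume 2". Nothing restricts a period's denominator to patients with data in that period.

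Other sections determine who has a Volume 2:

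- **SAP 4.17:** a locked Volume 1 is enough to make a patient a locked case, but "data from CRFs from which subsequent volumes are not locked will not be used in analyses".
- **SAP 4.2:** among patients who completed as discontinued, the definition of completing the observation period recognises "Separate volume 1 (official approval) and Separate volume 2 is “Unnecessary ” or“ Unable to collect".
- **Protocol 6**, on the observation period: "If a patient has withdrawn from /terminated administration of Benlysta, it will be until the withdrawal/termination".
- **Protocol 7, item 4:** CRF 1 covers Weeks 1–24 and CRF 2 covers Weeks 25–52. The booklet is submitted at the end of its period or at withdrawal.
- **Protocol 8, item 5:** prior SLE drugs are recorded as "name of drugs, from 4 weeks before the start of administration to the day before the start". The next sentence extends this to 24 weeks for other biologics and intravenous cyclophosphamide.

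On missing data, SAP 4.4.1 limits imputation to 4.4.2 (SELENA SLEDAI and PGA). SAP 4.4.4 keeps missing values in percentage denominators unless stated otherwise.

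**The concern.** The table is presented as a change over time, so a reader will compare the three percentages. The Volume 2 percentage mixes two quantities: how many patients with a Volume 2 used an immunosuppressant, and how many patients have a usable Volume 2. The second lowers the figure whatever the first does.

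A drop from Volume 1 to Volume 2 could therefore be taken as withdrawal of background immunosuppressants when it only reflects early discontinuation or missing booklets. A real increase could be hidden in the same way.

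Neighbouring outcomes are handled differently. For the steroid reduction endpoint at Weeks 40–52 (SAP 4.10), patients who stop before Week 52 count as non-responders, which lowers the success rate. For continuous data (SAP 4.4.3), a missing time point is left out of the tabulation. In Table 3.15, patients who stop by Week 24 stay in the Volume 2 denominator and lower apparent immunosuppressant use.

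**Working it through.** The documents state no figure for Table 3.15, so there is none to reproduce. The check is arithmetic.

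**Who lacks a Volume 2 record.** The efficacy set is a subset of the safety set, which is drawn from patients with locked CRFs (SAP 4.2). Locking Volume 1 suffices (4.17). The efficacy set can therefore include:

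1. patients who stopped by Week 24, whose observation ended before Volume 2 began;
2. patients whose Volume 2 was not collected;
3. patients whose Volume 2 was collected but not locked, so its data are not used.

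Patients who stopped in Weeks 25–52 are not in group 1, because they can have a Volume 2 submitted at withdrawal. Every member has a locked Volume 1, and an early stopper's Volume 1 still records drugs up to withdrawal, though over a shorter window.

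**Notation.**

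- d = share of the efficacy set without a locked Volume 2
- u_c = use among patients with a locked Volume 2
- u_d = use among those without one

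**Formulas**, with each patient's use unchanged over time:

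- Volume 1 rate = u_c(1 − d) + u_d·d
- Volume 2 rate as planned = u_c(1 − d)
- Volume 2 rate on locked Volume 2 patients = u_c

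**Case 1: same use in both groups (u_c = u_d = u).** The false fall is u − u(1 − d) = u·d, which is d in relative terms. The values of u and d are assumptions. False fall in percentage points:

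| u | d = 5% | d = 10% | d = 20% | d = 30% |
|---|---|---|---|---|
| 40% | 2.0 | 4.0 | 8.0 | 12.0 |
| 50% | 2.5 | 5.0 | 10.0 | 15.0 |
| 60% | 3.0 | 6.0 | 12.0 | 18.0 |

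The range is 2 to 18 points. The table is also broken down by drug, and for a drug used by 20% the fall at d = 10–30% is 0.20 × 0.10 to 0.20 × 0.30, or 2 to 6 points.

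**Case 2: different use in the two groups (assumed u_c = 50%, d = 20%).**

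- u_d = 70%: Volume 1 = 0.50 × 0.80 + 0.70 × 0.20 = 54%; planned Volume 2 = 0.50 × 0.80 = 40%.
- u_d = 30%: Volume 1 = 0.40 + 0.06 = 46%; planned Volume 2 = 40%.

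Nobody changes treatment in either example. With a locked Volume 2 denominator the series reads 54% to 50%, or 46% to 50%. The arithmetic artefact has gone, but a difference from selection remains. Pairing Volume 1 and Volume 2 in the same patients gives 50% to 50%.

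**Case 3: a hidden rise.** For the planned table to look flat at 50%, use among patients with Volume 2 must reach 0.50/(1 − 0.10) = 55.6% at d = 10%, or 0.50/(1 − 0.20) = 62.5% at d = 20%.

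**Windows.** For most SLE drugs the three periods are 4, 24 and 28 weeks. For other biologics and intravenous cyclophosphamide they are 24, 24 and 28 weeks. Where any use counts, the short prior window can make Volume 1 look higher than prior treatment for most drugs, but not for the 24-week rows.

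**The case against.** The best defence is that this is a descriptive table with no test or success criterion. Immunosuppressant reduction is not among the effectiveness items in Protocol 9, and the SAP nowhere calls Table 3.15 a sparing analysis. Numerators are printed, so a reader could rebase the percentages. The denominator sentence also appears in 6.2.3 and 6.2.4, where two sets are listed, so it may be carried-over text that the programmed table does not follow. All of this limits the consequence. It does not change what the rule says, and rebasing needs a Volume 2 count for the efficacy set. SAP 6.1.1 gives counts per volume only for collected, locked and safety-set patients.

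SAP 4.6 is also unclear on whether a patient with no drug record is classed as not using or as unknown. The dilution is the same either way, because 4.4.4 keeps unknowns in the denominator.

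Several stronger readings are tempting, and the documents do not support them:

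- *Volume 1 is diluted too.* It is not diluted by missing forms, since a locked Volume 1 is the condition of entry.
- *Everyone who stopped Benlysta is counted as a non-user.* Only those who stopped by Week 24, or who lack a locked Volume 2, are affected.
- *More treatment failure gives more apparent sparing.* Patients stop for many reasons and booklets go missing for others, so absence of Volume 2 is not failure.
- *This is the only table on immunosuppressant use.* Tables 1.04x, 1.05 and 1.051 also report use by drug. What is particular to Table 3.15 is the separate Volume 2 column and its presentation as a trend.
- *The prior period is 4 weeks throughout.* It is 24 weeks for other biologics and intravenous cyclophosphamide, and Table 3.15 includes biologics.

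**Conclusion.** The point holds for the Volume 2 column. As written, SAP 6.4.16 biases that rate downward and creates a false fall from Volume 1. The same dilution acts on the comparison with prior treatment, where unequal windows may pull the other way for most drugs.

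The relative size equals d if use is constant and unrelated to having a Volume 2. The absolute size cannot be computed from the documents. The 2–18 point range rests wholly on assumed use of 40–60% and d of 5–30%. If d proves very small the effect is negligible, but the plan as written would not show the reader that. The mock-up of the table is not available, so whether the programmed output follows the sentence is unknown.

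**What to change.** In SAP 6.4.16:

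1. Set the denominator for each period to efficacy-set patients whose booklet for that period is locked, and print n per period. Volume 1 is unchanged by this, since every member has it locked. Prior treatment is unchanged too if prior drugs are recorded in Volume 1.
2. Add a paired table in patients with a locked Volume 2, cross-tabulating use against non-use for prior treatment v Volume 2 and for Volume 1 v Volume 2.
3. State that the Volume 2 rate then describes patients who continued beyond Week 24 and had a locked booklet. It rests on fewer, selected patients and should be read with the paired table.
4. Footnote the windows: prior period 4 weeks for most SLE drugs and 24 weeks for other biologics and intravenous cyclophosphamide, against 24 weeks (Volume 1) and 28 weeks (Volume 2).

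The cost is a wording change, a row of counts and one small table from data already held. If Table 3.15 has already been produced, it needs one re-run.

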 - 2) After approval of Benlysta, the Written Contract should be concluded before the start of administration in principle, however, patients to whom Benlysta has unavoidably been administered before the conclusion of the contract will be also enrolled as a retrospective patient.
4. Data collection and case report form (CRF) completion
- 1) The investigator will confirm the study items, such as the characteristics of patients eligible for CRF collection.
 - 2) During the observation period, the investigator will monitor the information about safety and effectiveness, etc. If an enrolled patient does not visit the hospital during the observation period, the investigator will monitor the information about AEs and others by telephone, etc. as far as possible.
 - 3) The CRF consists of three CRFs to maximum, and the observation period per CRF will be defined as below.
 - CRF 1 : Week 1 to 24 after the start of administration
 - CRF 2 : Week 25 to 52 after the start of administration
 - Follow-up Investigation CRF : Year 1 to 3 after the start of administration
 - 4) The investigator will record the obtained information on the CRF. At the end of the observation period of enrolled patients for each CRF (or at withdrawal/termination, if a patient has withdrawn from /terminated administration of Benlysta), submit the completed CRF to the person in charge of the study. The personally identifiable information, such as the name, address, date of birth, initials of patients, should not be recorded in the CRF.
5. Confirmation of all-case investigation implementation
- Annually and after the end of the study period, the investigator will confirm whether or not enrolled patients are all receiving Benlysta, affix his/her signature or name/seal to the "Confirmation Letter of All-Case Investigation" and submit it to the person in charge of the study.

8. Study Items

The investigator will collect the information about the following items, etc. as far as possible and record it on the CRF.

1. Information about a medical institution
Name of a medical institution, department, investigator
2. Patient characteristics (at the start of administration of Benlysta)

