4.4.5. Date Variables

Imputation of date variables will be handled as follows.

< End date of administration of this drug >

- ✧ If the number of doses of this drug is once, imputation will use the start date of this drug administration.

< Adverse events >

- ✧ If the date of onset and date of outcome are missing, they will not be imputed and will be handled as unknown.

< Prior treatment drugs/Prior treatment (other than drugs)/Concomitant drugs >

- ✧ Only systemic steroids for SLE have a date but if the last record is ' Dosing Continued ', then it will be imputed with the last date from this drug Administration Status.

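### Table 3.15: conventional immunosuppressants are counted over 4 weeks before start but 24 weeks in Volume 1, so the first step is biased upward and cannot show withdrawal during Weeks 1 to 24

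*SAP*

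**What the plan says.** SAP 6.4.16 defines Table 3.15, on changes in the proportion of patients receiving immunosuppressants, in the efficacy analysis population. Numbers of users and usage rates are "calculated by immunosuppressant and immunosuppressant (biologic drug) for each drug code (GSKdrug) and generic name". The chronological order is "Prior treatment, Separate volume 1, Separate volume 2", and the denominator is the number of patients in the analysis set.

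The length of each period comes from the protocol:

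- **Prior treatment, SLE drugs in general** (Protocol section 8, item 5): "from 4 weeks before the start of administration to the day before the start".
- **Prior treatment, exception** (same item): "Biological preparations and cyclophosphamide (intravenous injection) except Benlysta will be monitored from 24 weeks before the start of administration".
- **Volume 1** (Protocol section 7, item 4): "CRF 1 : Week 1 to 24 after the start of administration". SAP 6.2.4 likewise ties Volume 1 to use until Week 24.
- **Volume 2** (Protocol section 7, item 4): "CRF 2 : Week 25 to 52 after the start of administration".

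For SLE drugs other than systemic steroids, Protocol section 8, item 7 collects whether a drug was used and its name, plus the route for cyclophosphamide. SAP 4.4.5 states: "Only systemic steroids for SLE have a date".

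**The concern.** With no dates, a patient counts as a user in a column if the drug was taken at any time in that column's window. Such a share grows with the length of the window. For conventional immunosuppressants, the column before Benlysta covers one sixth of the time covered by the first column on Benlysta, yet the table sets the two side by side as successive time points.

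Two misreadings are at stake. A higher Volume 1 share could be taken as added immunosuppression after starting Benlysta when use was stable. A flat or slightly higher share could be taken as evidence that immunosuppressants were not withdrawn in the first 24 weeks, although that step cannot show such withdrawal.

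**Working it through.** The plan gives no figure for this table, so there is nothing to reproduce.

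**Windows, counted from the protocol**

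| Drug group | Prior | Volume 1 | Volume 2 |
|---|---|---|---|
| Conventional immunosuppressants | 4 weeks | 24 weeks | 52 − 25 + 1 = 28 weeks |
| Biologics, IV cyclophosphamide | 24 weeks | 24 weeks | 28 weeks |

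For conventional drugs the ratio is 24/4 = 6 from prior to Volume 1, and 28/24 = 1.17 from Volume 1 to Volume 2.

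**Withdrawal, without a model.** A patient on a drug on the first day of Benlysta is a Volume 1 user even if it is stopped days later. The Volume 1 share therefore cannot fall below the share in use on that day, and every later start adds to it. If 50% are on a drug at the start and all stop before Week 24, Volume 1 still reads at least 50%. Only use that ended in the 4 weeks before start can lower Volume 1 relative to prior treatment.

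**Size of the window effect, with a model.** Assume no true change: constant point prevalence *p*, and start rate *r* per year among non-users, balanced by stops. Then

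share(*w* weeks) = *p* + (1 − *p*)(1 − exp(−*r w*/52)).

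Both *p* (10–60%) and *r* (0.05–0.4) are assumptions. Example with *p* = 50%, *r* = 0.1: prior 0.5 + 0.5(1 − exp(−0.1 × 4/52)) = 50.4%; Volume 1 with *w* = 24, 52.3%; Volume 2 with *w* = 28, 52.6%.

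| *p* | *r* | Prior | Volume 1 | Volume 2 | Volume 1 − prior | Volume 2 − Volume 1 |
|---|---|---|---|---|---|---|
| 60% | 0.05 | 60.2 | 60.9 | 61.1 | +0.8 | +0.2 |
| 10% | 0.05 | 10.3 | 12.1 | 12.4 | +1.7 | +0.3 |
| 50% | 0.1 | 50.4 | 52.3 | 52.6 | +1.9 | +0.4 |
| 30% | 0.2 | 31.1 | 36.2 | 37.1 | +5.1 | +1.0 |
| 10% | 0.4 | 12.7 | 25.2 | 27.4 | +12.4 | +2.3 |

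(Shares in %; differences in points, from unrounded shares.) Over the whole range the first step is +0.8 to +12.4 points. The top corner is extreme: holding 10% prevalence at *r* = 0.4 needs a stop rate of 0.4 × 0.9/0.1 = 3.6 per user-year, or a mean spell of 52/3.6 ≈ 14 weeks. For biologics and IV cyclophosphamide the first step is 0.0, because both windows are 24 weeks.

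**Volume 2.** Observation ends when Benlysta is stopped (Protocol section 6), and data from unlocked later volumes are not used (SAP 4.17), but the denominator stays the full set. If a fraction *m* has no Volume 2 data and usage is otherwise alike, the share is multiplied by (1 − *m*). For *p* = 50%, *r* = 0.1:

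- *m* = 10% gives 52.6 × 0.9 = 47.4%, and *m* = 20% gives 42.1%.
- *m* = 1 − (Volume 1 share/Volume 2 share) = 0.7% cancels the rise from Volume 1 to Volume 2 (0.2% to 8.3% over the whole range).
- *m* = 4.3% brings Volume 2 back to the prior share.

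**The case against.** The strongest reply is that little hangs on this table. Immunosuppressant use is not among the effectiveness items in Protocol section 9, SAP 6.4.16 specifies no test, and LLDAS compares immunosuppressants with prior medication through its own criterion (SAP 4.10). The columns are named by collection period, not by week, and the table shell, which is not in the documents, may already footnote the windows. The sizes are assumed throughout. The table is tabulated by drug, where start rates would be lower than for the class. Patients who leave early also have a shortened Volume 1 window, which softens the effect.

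Most of this stands as a limit on importance and size. It does not remove the defect: the SAP text calls the result a change, orders it chronologically and does not call for the windows to be stated. Even a drug with 10% prevalence and a start rate of 0.05 per year shows +1.7 points. The SAP avoids the problem for steroids by using the same 7-day window at every time point (SAP 4.12 and 4.13.2).

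A reader might infer three stronger things that the documents do not support:

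- **That the whole table is affected.** Other biologics and IV cyclophosphamide "will be monitored from 24 weeks before the start of administration to the day before the start", which equals Volume 1. Whether IV cyclophosphamide enters the table at all depends on class definitions held in a separate document (SAP 4.8).
- **That the recorded share keeps rising into Volume 2.** The extra 4 weeks add little, and the full-set denominator pushes the other way.
- **That withdrawal is hidden altogether.** A patient who stops during Volume 1 drops out of the Volume 2 column. There, however, the fall is mixed with patients who have no usable Volume 2 data.

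**Conclusion.** The point holds for conventional immunosuppressants and for the step from prior treatment to Volume 1. As specified, that step is biased upward under stable use and cannot register withdrawal during Weeks 1 to 24. The direction and the blind spot follow from the documents alone. The size, about 1 to 12 points, rests on the assumed prevalences and start rates and on the steady-state model, so it is an illustration rather than an estimate; the upper end needs very short spells of use.

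The point does not extend to biologics or IV cyclophosphamide, and it makes no claim of a rise into Volume 2. The net direction of the Volume 1 to Volume 2 step depends on how many patients lack Volume 2 data, which the documents do not say. Since the table is descriptive and the correction uses data already collected, this is something that should be changed before the final report, not a threat to the study's main conclusions.

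**What to change.** Revise SAP 6.4.16 and Table 3.15 as follows:

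1. For conventional immunosuppressants, present prior treatment as a baseline description, not as a time point in a trend.
2. Label every column as any use in the period and print its window (4, 24 or 28 weeks). Keep biologics and, if included, IV cyclophosphamide in a separate block with their 24-week look-back stated.
3. Compare Volume 1 with Volume 2 only in patients with both volumes locked.
4. In those patients, add for each drug the share of pre-start users with no record of it in Volume 2. Word it as not recorded in Weeks 25 to 52: under SAP 4.6, items other than adverse events are judged from whether details were entered, so a blank is not proof of stopping.
5. If new use is tabulated, define it as not recorded in the 4 weeks before start and do not read it as a trend. It keeps the short look-back, so intermittent or recently paused users would count as new.

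The cost is a change of SAP wording and one re-programmed table on existing data. The simple three-point trend is lost, and early discontinuers drop out of the transition table, so their number should be shown beside it.
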